AP Anterior-Posterior

AST Aspartate Aminotransferase

BED2 Biologically Equivalent Dose in 2 Gy fractions

BID Twice daily

BUN Blood Urea Nitrogen
CBC Complete Blood Count

CMP Comprehensive Metabolic Panel

CR Complete Response
CrCl Creatinine Clearance
CRF Case Report Form

CRT Radiation Treatment and Concurrent Cisplatin

CT Computed Tomography

CTCAE Common Terminology Criteria for Adverse Events

CTQA Clinical Trials Quality Assurance

CTV Clinical Target Volume

DLQI Dermatology Quality of Life Index

DLT Dose Limiting Toxicity

DSMB Data and Safety Monitoring Board EQD2 2 Gy-per-fraction Equivalent Dose

FACIT-F Functional Assessment of Chronic Illness Therapy-Fatigue

FACT-G Functional Assessment of Cancer Therapy-General

FACT-HN Functional Assessment of Cancer Therapy – Head & Neck (Version 4)

GMP Good Manufacturing Practice

GTV Gross Tumor Volume

Gy Gray

HIF-1 Hypoxia-inducible factor-1

HNSCC Head and neck squamous cell carcinoma

H&P History & Physical Exam

HRPP Human Research Protections Program

HRQoL Health-Related Quality of Life
IMRT Intensity Modulated Radiotherapy

IGRT Image-Guided Radiotherapy

kV Kilovoltage

KPS Karnofsky Performance Scale MDS Myelodysplastic Syndrome

MedDRA Medical Dictionary for Regulatory Activities
MnSOD Manganese Superoxide Dismutase

MOS Median Overall Survival

MRI Magnetic Resonance Imaging MTD Maximum Tolerated Dose

MV Megavoltage

NCI National Cancer Institute
NFkB Nuclear Factor Kappa B

NRG NRG Oncology OAR Organs at Risk

OMWQ-HN Oral Mucositis Weekly Questionnaire – Head & Neck

ORR Overall Response Rate

OS Overall Survival
PA Posterior-Anterior
PD Progressive Disease

PEG Prophylactic Gastrostomy Tube
PET Positron Emission Tomography

PFS Progression-free Survival

PFS-6 Progression-free Survival at 6 months

p.o. per os/by mouth/orally

PR Partial Response

PRO Patient-Reported Outcome

PRO-CTCAE Patient-Reported Outcome version of the Common Terminology Criteria for

Adverse Events

PRV Planning Risk Volume
PTV Planning Target Volume

QoL Quality of Life

RP2D Recommended Phase 2 Dose

RT Radiation Therapy
SAE Serious Adverse Event

SCCHN Squamous Cell Carcinoma Head and Neck

SD Stable Disease

SIB Simultaneous Integrated Boost

SOC Standard of Care
SOD Superoxide Dismutase

SQ Subcutaneous

TDP Torsades de pointes
UAP Unanticipated problems
ULN Upper limit of normal

VMAT Volumetric-Modulated Arc Therapy
XeQoLS Xerostomia-Related Quality of Life Scale

WBC White Blood Cells

WHO World Health Organization

3 Schema of Clinical Trial

A Phase 1/2 Trial of Concurrent Radiation Therapy, Cisplatin, and BMX-001 in Locally Advanced Head and Neck Cancer

[figure not shown]

Figure 1. Schema of Clinical Trial

Patient Population: (See Section 6 for Eligibility Criteria)

Pathologically proven diagnosis of head and neck cancer (squamous cell carcinoma) requiring radiation and concurrent cisplatin chemotherapy.

Sample Size Phase 1: 6

Maximum Sample Size Phase 2: 48

Post-op in the above schema refers to subjects who have had tumor resection and are being scheduled for post-operative radiation therapy and chemotherapy.

Definitive Therapy in the above schema refers to subjects who have not undergone tumor resection but are being scheduled for primary radiation therapy and chemotherapy designed to be the definitive approach to their treatment program.

4 Introduction

4.1 Head and Neck Cancer

4.1.1 Disease

In 2013 the American Cancer Society estimated there would be 50,000 newly diagnosed cases of head and neck squamous cell carcinoma (HNSCC). Radiation therapy and concurrent cisplatin (CRT) play a prominent role in the treatment of this disease [1]. This regimen is effective in killing the tumor; however, the normal tissues in the mouth and throat are highly sensitive to radiation that can lead to severe side effects [2]. These side effects include: xerostomia (dry mouth), mucositis (inflammation and sores forming in the mouth), swelling, dysphagia, pain, infections, cavities, hair loss, and reddening of the skin. Some of these side effects may be severe enough to require feeding tube placement and detrimentally prolong the time required to complete a course of therapy. Amifostine (Ethyol®) is the only FDA approved radioprotector against radiation-induced xerostomia. Its value in preventing this side effect in a CRT setting is uncertain and it has minimal effect against mucositis.

4.1.2 Radiation-induced Damage

Radiotherapy for the treatment of head and neck cancers can produce severe therapy-induced side effects. Acute effects commonly appear within a week of starting radiotherapy and most people suffer from at least one of these unwanted side effects. The acute side effects can include: xerostomia, mucosal degradation (mucositis) and ulceration, edema, loss of taste (dysgeusia), difficulty swallowing and talking, ear aches, infections, hair loss, and radiation dermatitis. These acute problems can become so severe that radiation therapy has to be delayed, which can lead to reduced local control or at times, terminated. Long-term complications from radiation therapy directed to the head and neck region can include trismus (restriction on opening of the jaw), osteoradionecrosis, or breakdown of the mandible, loss of sensation, loss of taste, increased risk of dental caries (cavities), and decreased salivary function. Thus, quality of life can be severely compromised following the treatment of head and neck cancers. More concerning is the increase in non-cancer-related deaths in patients treated with concurrent high dose cisplatin and radiation in RTOG 91-11 as a result of long-term complications. This damage can occur anytime during radiation therapy and has been reported years after treatment. The long-term toxicities are a function of high dose radiation and volume of irradiated tissue, amplified by the addition of radio-sensitizing chemotherapy. Once the damage of normal tissue begins, it is usually progressive and irreversible. Because there is a 50-85% five year survival rate for patients treated for head and neck cancers, due in part to a rapidly increasing segment of younger patients experiencing HNSCC related to human papillomavirus infection, there are many people who are living with these long-term side effects (American Cancer Society, 2013 Statistics). Thus, the development of an effective radio-protector would improve the quality of life of many head and neck cancer patients.

4.2 BMX-001

It is well established that induction of oxidative stress after radiation therapy (RT) and chemotherapy plays a major role in tumor and normal tissue therapy responses [3,4]. Ironically, the responses in tumor tend to protect vascular endothelium and tumor cells from RT damage [5], whereas these same stresses after RT promote normal tissue damage [3,6]. A variety of approaches have been investigated to mitigate oxidative stress post irradiation, including the

free radical scavenger, amifostine [7-9]. Although this agent is approved for this use, its daily use is limited by side effects [7-9]. In addition, this agent was used primarily to protect salivary tissue rather than as a protectant against mucositis or dermatitis and with the advent of salivary sparing radiation techniques, this approach has fallen out of favor. Other agents that have been tested pre-clinically and clinically include nitroxides and genistein, but these are not currently approved for protection against normal tissue injury post-irradiation and neither provides catalytic inactivation of reactive species responsible for oxidative stress [7]. Over the past 20 years, [name] and colleagues have developed a class of manganese (Mn) Porphyrin-based compounds that: 1) are potent anti-inflammatory agents and 2) catalytically inactivate a range of reactive oxygen species, including peroxynitrite and superoxide anion [10-12]. These properties give this class of compound the unique function of protecting normal tissues while also augmenting tumor killing in patients undergoing radiation and chemotherapy. In addition to inactivation of reactive oxygen species, these drugs inhibit transcriptional activity of stress-induced pathways by either eliminating reactive oxygen species that activate stress responses or by indirectly preventing activation. Transcription factors known to be inhibited by this class of metalloporphyrin include HIF-1 [13,14], NFkB [15], SP-1 [16] and AP-1 [10]. The most recently developed compound, BMX-001 (MnTnBuOE-2-PyP5+), is among the most highly potent in a series of well over two dozen metalloporphyrins that have been evaluated thus far [17]. BMX-001 is lipophilic and crosses the blood-brain barrier. This drug has been licensed for commercial development and will be the lead compound for this project.

Metalloporphyrins have been shown to protect mice from total body irradiation toxicity [18] and xerostomia following parotid gland irradiation [19]. Radiation-induced lung injury was protected against by administration of metalloporphyrins in rhesus macaques [20]. Additionally, metalloporphyrins have been shown to protect against a range of CNS conditions associated with inflammation, including stroke [21] and spinal cord damage [22-24]. Relevant to this application, Dewhirst and colleagues showed protection against inflammation (mucositis) and decreased saliva production (xerostomia) after a single dose of 13 Gy RT. In this study, C57BL/6J mice were exposed to 13 Gy of irradiation with and without concurrent BMX-001. At 10 days post-RT, mice that had been treated with BMX-001 and RT had decreased mucositis as measured by an inflammation-detecting fluorescent probe, ProSense 750EX, in comparison to mice that received only RT without BMX-001. Additionally, at 6 weeks post-RT, xerostomia was not as pronounced in animals treated with BMX-001 as compared to mice that received only RT without BMX-001. Thus, saliva production ability was preserved and salivary inflammation was prevented in mice irradiated with 13 Gy and treated with BMX-001.

In tumors, Dewhirst and colleagues showed that RT and chemotherapy increase oxidative stress, driving upregulation of HIF-1 [5,25], a transcription factor that promotes endothelial and tumor cell survival and increases tumor aggressiveness [26]. Radiation creates persistent oxidative stress in surviving cells, which upregulates NFkB [27]; this transcription factor also drives treatment resistance [28]. Treatment with this new class of metalloporphyrin prevents HIF-1 and NFkB upregulation in tumors after RT and chemotherapy and improves tumor treatment responses [18]. The effect of BMX-001 has been studied on mouse flank xenografts using human hypopharnygeal squamous cell carcinoma (FaDu). In this study by Dewhirst and colleagues, FaDu tumor size was not significantly changed in the presence of BMX-001 without irradiation. However, in the presence of irradiation, BMX-001 significantly inhibited FaDu growth in nude mice. In addition, BMX-001 significantly increased the survival of the tumor bearing animals. The average time to euthanasia (tumor volume>1500 mm³) for irradiated alone animals was 49.8

days, and mice irradiated with BMX-001 had an average survival of 63 days. Thus, BMX-001 did not protect head and neck tumor cells from radiation sensitization; in fact, BMX-001 further sensitized the head and neck tumor to irradiation and enhanced the survival of tumor bearing animals. This demonstrates that BMX-001 has differential effects in tumor tissue compared to normal tissues, with BMX-001 showing potential to protect normal tissues and sensitize tumors to RT. Thus, the rationale for this protocol is based on the demonstrated dual activity of BMX-001 to protect normal tissue while sensitizing tumors to therapy [19].

Preclinical safety toxicology studies have shown a No Observable Effect Level (NOEL) in mice of 12 mg/kg and in cynomolgus monkeys of 2 mg/kg. BioMimetix has concluded a Phase 1 dose escalation study in newly diagnosed high-grade glioma patients. This clinical trial has demonstrated no adverse effects in subcutaneous dosing up to 28 mg/subject load with half the loading dose given biweekly for 8 weeks in 12 subjects. Three subjects were enrolled and dosed with 42 mg/subject load with half the loading dose given biweekly for 8 weeks. Of these three subjects, there was one dose-limiting toxicity of grade 3 tachycardia and grade 3 hypotension. The DLT in this subject occurred with the loading dose (42 mg sc). The patient was treated with fluids and hospital admitted for observation for 24 hours during which time the hypotension and tachycardia resolved. The cardiac rhythm was a sinus tachycardia and no other cardiac toxicity was observed. The tachycardia was assumed to have resulted from hypotension occurring following the sub-cutaneous injection of BMX-001 (42 mg). After the loading dose of BMX-001 and the described DLT, the subject continued on study and experienced no tachycardia or hypotension following administration of the subsequent 16 maintenance doses (20 mg sc).

The most common related toxicity see in this Phase 1 trial was injection site reaction and all of these have been grade 1. There is no apparent toxicity to end organ tissues or bone marrow.

The completion of a Phase 1 clinical trial in patients with high-grade glioma undergoing brain radiation therapy plus chemotherapy with temozolomide has established an MTD for BMX-001. The MTD by sub-cutaneous injection is 28 mg/subject load followed by a maintenance dose of 14 mg/subject b.i.w. At the MTD, there have been no BMX-001 dose limiting toxicities observed.

Based on the completion of Phase 1 and establishment of an MTD for this treatment regimen in patients undergoing radiation therapy and chemotherapy, this clinical trial of head and neck cancer patients will proceed to a Phase 2 trial of 48 subjects with a safety lead-in of 6 subjects. The reason for the safety lead-in is to confirm safety in subjects receiving radiation therapy to the head and neck area and with chemotherapy involving cisplatin.

4.3 Study Design

This study will involve escalating doses of BMX-001 with standard of care concurrent RT and cisplatin. Patients with biopsy-proven head and neck cancer (squamous cell carcinoma) will undergo standard staging consisting of history and physical exam, contrast enhanced CT +/- PET scan and/or MRI, and QoL questionnaires. Intensity modulated radiotherapy (IMRT) will be delivered with once daily 2.0-2.1 Gy fractions for definitive intent or adjuvant post-operative patients requiring chemo-radiation for high-risk disease including evidence of positive margins or extracapsular lymph node extension. Patients undergoing definitive intent IMRT will receive 69.3-70 Gy in 33 -35 fractions. Post-operative IMRT will be delivered to a dose range of 60-66 Gy in 30-33 fractions.

Cisplatin will be delivered per investigator choice, either 100 mg/m² IV q21 days x 2, 100 mg/m² IV q21 days x 3, or 30-40 mg/m² IV weekly x 6-7 doses. All of these dosing schedules are

acceptable as standard of care per NCCN guidelines and utilized within NCI-sponsored cooperative groups [29]. A minimum of 3 subjects and a maximum of 54 subjects with locally advanced head and neck cancers will be enrolled into this study during a 48-month period.

4.3.1 **Phase 1- Completed**

We have conducted a dose-escalation study of BMX-001 in combination with standard dose intensity modulated radiation therapy (IMRT) and concurrent cisplatin (CRT) to determine the safety of the investigational drug, BMX-001 with concurrent cisplatin and radiation therapy. Since a RP2D of 28 mg/subject load/14 mg/subject maintenance (Dose Level 3) has recently been confirmed in a Phase 1 trial of BMX-001 (with Temozolomide for chemotherapy and brain radiation as opposed to the cisplatin and head/neck radiation to be completed in this trial). This Phase 1 trial in head and neck cancer patients was only completed through Dose Levels 1 and 2. Patients with locally advanced (stage III-IVB) HNSCC for whom radiation plus cisplatin is appropriate were eligible based on inclusion and exclusion criteria. Subjects were administered BMX-001 subcutaneously as a loading dose on day -4 to 0. Starting on day 1 or 2 of CRT patients received a maintenance dose (50% of loading dose) twice weekly administered on days of radiation therapy and for one week after radiation concluded. Cisplatin was administered per institution's standard of care practice. Common standard of care practice includes dosing cisplatin at 100mg/m² IV q21 days starting on Day 1 of RT for 2-3 doses or dosing cisplatin at 30-40 mg/m² IV on Monday or Tuesday of each week of RT for 6-7 total doses. Patients received a continuous course of IMRT delivered as single daily fractions of 2.0 -2.1 Gy with a cumulative radiation dose between 60 Gy and 70 Gy depending on whether they have undergone resection or are receiving definitive radiation therapy. Planned radiation treatment volumes included at least two oral sites (buccal mucosa, floor of mouth, oral tongue, soft palate, hard palate, retromolar trigone) with each site receiving a minimum total of 50 Gy.

In order to evaluate the pharmacokinetics (PK) of BMX-001, blood samples were drawn for analysis.

Cohorts of 3 subjects have been accrued with dose escalation, beginning with 7 mg/subject load and ending with 14 mg/subject load. Following the treatment of 3 subjects at dose levels 1 and 2, and with no BMX-001 related dose limiting toxicities as defined in this protocol, the Phase 1 portion is completed.

4.3.2 Phase 2

We will do a safety lead-in trial for head and neck cancer patients involving 6 subjects at the 28 mg/subject loading dose given by subcutaneous injection followed by one-half the loading dose (14mg/subject) administered by subcutaneous injection biweekly during the remainder of the trial. We will assess safety in a lead-in cohort of 6 head and neck cancer patients being treated with cisplatin and radiation therapy. Once those 6 subjects are enrolled, we will then move to full Phase 2 open enrollment. Based on the preclinical safety toxicology studies in mice and monkey and the results of the Phase 1 BMX-001 high-grade glioma trial in humans, we anticipate that a dose of 28 mg/subject load followed by one-half the loading dose (14 mgs) twice weekly will not have dose-limiting toxicities in patients enrolled in this study. If this expectation is confirmed (meaning there are no definite BMX-001-related dose-limiting toxicities, defined as grade 3 study-drug-related adverse events), this dose will be utilized in the full Phase 2 trial enrolling an additional 42 subjects. If one or more definite BMX-001 related grade 4 or 5 DLTs occur in the 6 patient safety lead-in cohort, accrual will pause pending review by the sponsor and DSMB. Non

BMX-001 related DLTs are anticipated in this patient population due to the primary disease and treatment regimen.

This is not a randomized trial. All eligible patients enrolled will receive BMX-001.

A maximum of 48 patients will be enrolled in this Phase 2 clinical trial.

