11.11 Dose-Limiting Toxicity (DLT)

Toxicities will be graded according to the NCI CTCAE version 4.03 criteria. DLTs will be defined as any of the following events that are at least (possibly, probably, or definitely) attributable to BMX-001 during the study. The DLT period includes from the start of BMX-001 through 4 weeks after CRT concludes.

A dose limiting toxicity is defined as an adverse event or laboratory abnormality that is: a) assessed as unrelated to disease progression, intercurrent illness, or concomitant medications; b) occurs during and/or following the first dose of BMX-001; and c) meets any of the following criteria:

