11.11.1 Non-hematologic

The occurrence of non-hematologic grade 3 or greater adverse events considered to be possibly, probably, or definitely related to BMX-001 during treatment with BMX-001, excluding grade 3 alopecia and elevation in alkaline phosphatase, grade 3 nausea or vomiting unless occurring despite the use of standard anti-emetics.

> 14 day delay to re-treat due to failure to resolve any grade 3 or greater non-hematologic drugrelated toxicity to re-treatment criteria or pre-treatment baseline.

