14.1 Adverse Events

An adverse event (AE) is any untoward medical occurrence in a subject receiving study drug and which does not necessarily have a causal relationship with this treatment. For this protocol, the definition of AE also includes worsening of any pre-existing medical condition. An AE can therefore be any unfavorable and unintended or worsening sign (including an abnormal laboratory finding), symptom, or disease temporally associated with the use of BMX-001, whether or not related to use of the BMX-001. Abnormal laboratory findings without clinical significance (based on the Pl's judgment) should not be recorded as AEs, but laboratory value changes that require therapy or adjustment in prior therapy are considered adverse events.

From the time the subject signs the informed consent form through the End of Treatment visit (as defined in the section titled End of Treatment), all AEs must be recorded in the subject medical record and adverse events case report form.

AEs will be assessed according to the CTCAE version 4.03. If CTCAE grading does not exist for an AE, the severity of the AE will be graded as mild (1), moderate (2), severe (3), life-threatening (4), or fatal (5).

Attribution of AEs will be indicated as follows:

- Definite: The AE is clearly related to the study drug
- Probably: The AE is likely related to the study drug
- Possible: The AE may be related to the study drug
- Unlikely: The AE is doubtfully related to the study drug
- Unrelated: The AE is clearly NOT related to the study drug

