14.3 External Data and Safety Monitoring Board (DSMB)

The sponsor and Principal Investigators are responsible for overseeing the safety and efficacy of the trial, executing the DSM plan, and complying with all reporting requirements to local and federal authorities. Additional oversight will be carried out by an external DSMB.

An external DSMB will be utilized to monitor the Phase 1/Phase 2 clinical trial of BMX-001. This DSMB will be organized to meet requirements of Western IRB, the institutional IRBs, and the NCI. We anticipate a charter with a minimum of 3 members, which may include: a radiation oncologist, a medical oncologist both with expertise in head and neck cancer, a biostatistician, and/or an ethicist or patient advocate. The DSMB will hold an initial meeting to review the final protocol before enrollment of the first patient. The responsibilities of the DSMB will be to review safety of study procedures, to maintain study integrity, to review adverse events and to review efficacy of the outcome data. The DSMB will meet either face to face or by teleconference at least semi-annually and on an ad hoc basis as indicated by any adverse events. Minutes will be kept of both open and closed meetings of the DSMB. At the end of the study, all minutes taken will be available to the clinical trial principal investigators, the NCI, and BioMimetix JV, LLC.

During Phase 2 of the trial, the sponsor will notify the DSMB within 48 hours of any reported grade 3-5 DLT deemed probably or definitely related to BMX-001.

The DSMB's responsibilities will include evaluation of treatment outcome for evidence of tumor protection by the study drug. If the DSMB determines that there is substantial evidence of excess tumor progression in the presence of the study drug, the DSMB will have authority to recommend closure of the clinical trial.

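### Sections 4.3.2, 11.11 to 11.11.2 and 14.3 contradict each other on which BMX-001-related events count, so the lead-in could be declared free of DLTs when DLTs under 11.11 have occurred

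*Combined protocol and SAP*

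**What the plan says.** **Definition (11.11, 11.11.1, 11.11.2).** The general rule is: "DLTs will be defined as any of the following events that are at least (possibly, probably, or definitely) attributable to BMX-001 during the study". For non-hematologic toxicity it covers "non-hematologic grade 3 or greater adverse events considered to be possibly, probably, or definitely related to BMX-001", with a short list of exclusions. Section 11.11 also requires that the event be judged not to stem from progression, another illness or other medication. Section 11.11.2 sets separate hematologic criteria; neutropenia without fever counts only at grade 4.

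**Lead-in decisions (4.3.2).** The 28/14 mg dose goes forward to a further 42 subjects if the expectation of no dose-limiting toxicity is confirmed, "meaning there are no definite BMX-001-related dose-limiting toxicities, defined as grade 3 study-drug-related adverse events". The pause rule follows: "If one or more definite BMX-001 related grade 4 or 5 DLTs occur in the 6 patient safety lead-in cohort, accrual will pause". Sponsor and DSMB review would then take place.

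**Notification (14.3).** During Phase 2, "the sponsor will notify the DSMB within 48 hours of any reported grade 3-5 DLT deemed probably or definitely related to BMX-001".

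**Attribution scale (14.1).** The categories are separate: "Definite: The AE is clearly related to the study drug" and "Probably: The AE is likely related to the study drug", followed by Possible, Unlikely and Unrelated.

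**The concern.** Three attribution standards apply to what is nominally the same event: possible or higher to define it, probable or higher to notify the DSMB within 48 hours, and definite to act on it in the lead-in. Section 4.3.2 does not refer to 11.11. It supplies its own definition, and the grade wording differs as well as the attribution.

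The lead-in exists to confirm safety of this dose with cisplatin and head and neck radiation (end of 4.2). The Phase 1 cohorts in this trial stopped at 14 mg loading and 7 mg maintenance (4.3.1, 11.5), so the lead-in is this trial's first assessment of 28/14 mg in these patients. Phase 1 was closed on the absence of related DLTs under the protocol's own definition (4.3.1). A lead-in reported as free of definite DLTs would not extend that statement, although it would read as if it did. One event could also bar a patient from re-treatment as a DLT (13.2) while not counting in the decision about the cohort.

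**Working it through.** The plan states no operating characteristic for the lead-in rule, so there is no figure to reproduce. The check applies each rule literally to a non-hematologic event that meets 11.11.1, falls under none of its exclusions and passes the other-causes filter in 11.11.

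| Grade and attribution | DLT (11.11) | Fails expansion condition (4.3.2) | Pauses accrual (4.3.2) | 48-hour DSMB notice (14.3) |
|---|---|---|---|---|
| 3, possible | yes | no | no | no |
| 3, probable | yes | no | no | yes |
| 3, definite | yes | yes | no | yes |
| 4 or 5, possible | yes | no | no | no |
| 4 or 5, probable | yes | no | no | yes |
| 4 or 5, definite | yes | only if the 4.3.2 wording is read as grade 3 or higher | yes | yes |

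Three things follow.

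1. Because 14.1 separates probable from definite, a grade 5 event rated probable is a DLT that the DSMB hears of within 48 hours, yet it meets neither trigger in 4.3.2.
2. A grade 4 or 5 event rated possible is a DLT that triggers neither the pause nor the 48-hour notice.
3. The grade wording conflicts independently of attribution. Section 4.3.2 says grade 3, while 11.11.1 says grade 3 or greater. A definite grade 3 neutropenia without fever would fit the 4.3.2 wording but would not meet the neutropenia criterion in 11.11.2.

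Section 4.3.2 also expects DLTs that are not related to BMX-001. Under 11.11 no such event can exist, since attribution to BMX-001 is part of the definition. The two sections therefore use one name for two concepts.

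**Illustration only.** Let p be the per-patient risk of any 11.11 DLT and f the share of those rated definite. Both are assumed; the documents give neither. With six independent subjects, the chance of at least one counted event is 1 − (1 − p)^6 under 11.11 and 1 − (1 − pf)^6 if only definite events count (reading the 4.3.2 grade wording as 3 or higher).

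- p = 0.05, f = 0.5: 1 − 0.95^6 = 0.265 against 1 − 0.975^6 = 0.141.
- p = 0.20, f = 0.2: 1 − 0.80^6 = 0.738 against 1 − 0.96^6 = 0.217.
- p = 0.20, f = 0.5: 0.738 against 1 − 0.90^6 = 0.469.

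These concern any 11.11 DLT and do not describe the pause rule. For that rule, p must be the risk of a grade 4 or 5 DLT. With p = 0.10 and a quarter rated definite, the figures are 1 − 0.90^6 = 0.469 against 1 − 0.975^6 = 0.141.

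**The case against.** The three sections do different jobs: one defines, one sets a decision, one sets a notice. A broad definition with narrower triggers for action is a recognisable tiered design, and 4.3.2 gives a reason for it, namely that the disease and background regimen will cause severe toxicity anyway. That would answer the point if 4.3.2 took the 11.11 definition and then narrowed it openly. It redefines the term instead, and the filter in 11.11 already addresses other causes. The text does not say whether cisplatin, which section 10 treats as a study drug, falls under that filter.

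A reader might infer that a fatal event rated probable would go unseen. The documents do not support that. It reaches the DSMB within 48 hours, the DSMB can meet ad hoc (14.3), treatment-related serious events go to the sponsor within 24 hours (14.2.1), and the sponsor or investigator can end the study (13.6.1). What stands is that none of these makes accrual pause or blocks expansion.

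A reader might also infer that final safety reporting would be limited to definite events. It would not: 16.2.2.1 describes adverse events regardless of causality and has the manuscript tabulate possible, probable and definite ones. The gap lies in the lead-in decision and how it is described.

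Nor can one say that the definite category will hardly be used. The BMX-001 toxicities that the protocol anticipates are tied to the injection (11.10, 11.12), and the one DLT reported from the glioma trial occurred with the loading dose. Such events could plausibly be rated definite.

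**Conclusion.** The contradiction is real and rests on the text alone: two attribution standards separate the definition from the lead-in decisions, a third governs DSMB notice, and the grade wording differs between 4.3.2 and 11.11.1 to 11.11.2. Followed literally, the lead-in can be declared free of DLTs when DLTs under 11.11 have occurred.

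Its numerical size is unknown. It would be tempting to conclude that the rule misses most DLTs, but that requires an assumed DLT rate and a low share rated definite. The observed record gives no support for a high rate: 4.2 reports no BMX-001 DLTs at the same dose in glioma patients, and 4.3.1 reports none at the two lower doses here. The gap narrows as the definite share rises and disappears when that share is one.

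It would also be tempting to conclude that 11.11 is right and 4.3.2 wrong. The documents do not settle which standard was intended.

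Section 11.10.4 suggests that 28 mg dosing in this study had begun by the time of this amendment. The point still applies, because these rules govern how the lead-in is judged and reported, and 14.3 applies throughout Phase 2.

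**What to change.** The sponsor and DSMB should reconcile 4.3.2, 11.11 to 11.11.2 and 14.3:

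- define DLT once, and have 4.3.2 and 14.3 refer to that definition instead of restating it;
- state explicitly which attribution and grade standard governs each of the three actions: expansion, accrual pause and DSMB notice. If the tiers are meant to differ, say so and give the reason;
- remove or reword the reference in 4.3.2 to DLTs unrelated to BMX-001;
- report the lead-in result with the standard named, so that it can be set beside the Phase 1 statement.

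This review does not choose the threshold.

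The cost is a wording amendment. If the reconciled standard is wider than definite, more events may go to sponsor and DSMB review, and the expansion condition may fail more often. Section 4.3.2 currently names no action when that condition fails without a pause trigger, so the amendment should address that case too. The pause as written leads only to review, so aligning the wording creates no automatic stop.
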